- PSA progression requires a PSA rise above the threshold measured at any time point since the threshold was reached.

3.1.11 PSA doubling time between 3 and 12 months. PSA calculation requires at least two consecutive PSA rises (PSA2 and PSA3) above the threshold PSA (at least 3 PSA values); PSA2 and PSA3 must be obtained within 12 months of study entry. All baseline PSAs should be obtained at the same reference lab. Patient's PSA doubling time must be calculated using the following formula (<http://www.mskcc.org/nomograms/prostate/psa-doubling-time>):

$$\text{PSADT in days} = \frac{0.693 (t)}{\ln (PSA3) - \ln (PSA2)}$$

Where t = the number of days between PSA3 and PSA2

ln = the natural log

PSADT in months = PSADT in days divided by 30.4375

3.1.12 ECOG performance status 0 to 2.

3.1.13 Ability to swallow the study drugs.

3.1.14 Subjects must have normal organ and marrow function as defined below:

- Absolute neutrophil count $\geq 1,000$ /mL
- Hemoglobin ≥ 10 g/dL
- Platelets $\geq 100,000$ /mL
- Total bilirubin within normal institutional limits
- AST(SGOT)/ALT(SGPT) ≤ 1.5 X institutional ULN
- Creatinine clearance ≥ 60 mL/min/1.73 m²
- Hgb A1c $\leq 6.5\%$

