3.2 Exclusion Criteria

3.2.1 Evidence of metastatic disease on imaging studies (CT, x-ray, and/or bone scan).

3.2.2 Diagnosis of diabetes mellitus defined as:

- Fasting blood glucose > 126 mg/dl or,
- Random blood glucose > 200 mg/dl
- Hemoglobin A1C $> 6.5\%$

- 3.2.3** Need for treatment with any conventional modality for prostate cancer (surgery, radiation therapy, and hormonal therapy).
- 3.2.4** Treatment with any investigational drug 30 days prior to randomization.
- 3.2.5** Radiation therapy within prior 6 months (prophylactic radiotherapy to prevent gynecomastia within 4 weeks prior to randomization is allowed).
- 3.2.6** Known hypersensitivity to metformin.
- 3.2.7** Prior history of lactic acidosis.
- 3.2.8** Any history of myocardial infarction in the past 12 months.
- 3.2.9** Subjects who consume more than 3 alcoholic beverages per day.
- 3.2.10** Subjects with serious intercurrent illness, including, but not limited to, ongoing or active infection, symptomatic congestive heart failure, unstable angina pectoris, cardiac arrhythmia, or other nonmalignant medical or psychiatric illness that is uncontrolled or whose control may be jeopardized by the complications of this therapy or may limit compliance with the study requirements (at the discretion of the investigator).
- 3.2.11** Patient with previous or concurrent malignancy. Exceptions are made for patients who meet any of the following conditions: Basal cell or squamous cell carcinoma of the skin or prior malignancy that has been adequately treated and patient has been continuously disease free for ≥ 2 years.
- 3.2.12** Subjects currently treated with metformin and/or bicalutamide or who have been treated with metformin and/or bicalutamide in the past 6 months.
- 3.2.13** Subjects who have taken 5 α -reductase inhibitors (finasteride or dutasteride), saw palmetto, or PC-SPES within the last 6 weeks are ineligible. Subjects will be eligible for the study after the wash out period of 6 weeks.

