5.5 Dose Modifications

All toxicities should be graded according to the Version 4.0 of the NCI Common Terminology Criteria for Adverse Events (CTCAE). Dose modifications will be based on the highest grade since the prior dose and will be performed as outlined below depending on the type and severity of the toxicity encountered, provided that the criteria have not been met for subject withdrawal from study. Patients will be withdrawn from the study if they fail to recover to CTCAE grade 0-2 (or within 1 grade of starting values of pre-existing laboratory abnormalities) from a treatment related toxicity within 4 weeks. Treatment may be delayed no more than 4 consecutive weeks to allow recovery from toxicity or the patient will be removed from the study. Dose modifications are not necessary for Grade 1 or 2 toxicities. The reason for dose modification, delay, and missed doses must be detailed in the source document. Dose re-escalation will not be allowed during this study.

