Hepatic dysfunction* AST or ALT=1.8- 3.0 X ULN		Repeat AST & ALT in 2 weeks. If either AST or ALT > 1.8 X ULN, continue at discretion of Investigator, monitoring AST & ALT every two weeks until both < 1.8 X ULN – then resume annual testing. If Investigator decides to stop medication, resume once AST & ALT < 1.8 X ULN, starting with 500 mg BID for 4 weeks, then increasing to 2 tablets per day with annual AST & ALT assessments
Hepatic dysfunction* AST or ALT > 3.0 X ULN		Hold study drug. Repeat LFTs in 2 weeks. If AST and ALT < 1.8 ULN, resume medication. Resumption involves 500 mg BID for 4 weeks, then increase to 1000mg BID per day with resumption of protocol specified monitoring if both AST and ALT remain at < 1.8 x ULN. If repeat AST and ALT are 1.8-3.0 x ULN, follow steps as described in section above. If AST and/or ALT > 3.0 x ULN, initiate workup for liver disease. If AST or ALT=1.8-3.0 resume medication at the discretion of the investigator.
Renal dysfunction Creatinine > 115 µmol/L 1.3 mg/dL		Hold study drug for up to 4 weeks. After resolution of event, use ramp-up schedule.
Clinical diagnosis of congestive heart failure	> Grade 3	Hold study drug for up to 4 weeks. Re-start may be considered if underlying condition (e.g. acute MI) has resolved. If Metformin is started after CHF, the ramp-up schedule should be used. Do not re-start if symptoms persist or ongoing treatment of CHF is required.
Acidosis (Lactate > 5.0 mM) (pH < 7.3)	Grade 3	Stop study drug and do not re-start. Report as a serious adverse event.
Anemia Hgb < 110 or MCV > 105	> Grade 1	Perform CBC and serum B12 level. Initiate anemia workup if cause of anemia not apparent. Continue at full dose. (Treatment is not held for anemia regardless of toxicity grade.)
Skin Reactions Major – generalized urticaria, bullous rashes, exfoliative dermatitis	Generalized	Stop study drug and do not re-start

Stevens Johnson Syndrome Localized	Localized	Hold study drug for up to 4 weeks if possibly, probably or definitely related to study drug. When rash clears, 500 mg BID per day for 4 weeks, then 1000 mg BID per day – if rash recurs, and is thought to be possibly, probably or definitely related to study medication, discontinue study medication.

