11.5 Safety Analyses

Safety analyses will be conducted on treated patients. All adverse events will be summarized 1) without regard to causal relationship and 2) by causal relationship to study drugs, based on the Investigator's opinion. Worst toxicity grades per subject will be tabulated for selected adverse events and laboratory measurements. Any serious adverse event or

adverse event resulting in premature and permanent discontinuation of any study drug will be described in detail. Adverse events and other symptoms will be graded according to the National Cancer Institute (NCI) Common Terminology Criteria for Adverse Events (CTCAE) Version 4.0

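### Section 11.5 tabulates the worst laboratory grade without reference to the screening value, so unchanged mild abnormalities present at entry would be counted as toxicity in both arms

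*Combined protocol and SAP*

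**What the plan says.** Section 11.5 (Safety Analyses) states the population, "Safety analyses will be conducted on treated patients", and the laboratory summary, "Worst toxicity grades per subject will be tabulated for selected adverse events and laboratory measurements". Grading is by CTCAE version 4.0. Section 11 contains no baseline definition, shift table or condition that a grade be new or worse than at screening. The adverse event definition in Section 10.1.1 includes abnormal laboratory findings and adds no such condition either.

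Section 3.1.14 is introduced by "Subjects must have normal organ and marrow function as defined below", but several of its limits lie outside normal. Hemoglobin may be as low as 10 g/dL, and AST/ALT may reach "1.5 X institutional ULN". Only bilirubin must be within normal limits. No entry limit is set for MCV or vitamin B12.

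Elsewhere the protocol does use the starting value. Section 5.5 allows recovery to be judged "within 1 grade of starting values of pre-existing laboratory abnormalities", and Section 5.9 accepts return to baseline severity as resolution of an adverse event.

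**The concern.** A worst-grade table answers how abnormal each man ever was. A reader of a safety section wants to know how many men became worse. The two agree only if everyone starts at grade 0, and the entry criteria do not ensure that.

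Hemoglobin shows this from the documents alone, because the eligibility range and the anemia row in Section 5.5.1 overlap. Section 10.1.3 also lets the protocol's own toxicity tables define severity alongside CTCAE. Vitamin B12 is a second case: Section 1.3 names low B12 as a metformin effect, and Table 1 in Section 6.1 measures it at screening and off treatment. If it is among the selected measurements, a low final value says little unless set against the first.

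Safety and tolerability of metformin is a secondary endpoint (Section 2.2), to be read from nominally 22 men in arm A and 44 in arm B. At that size a few pre-existing abnormalities can make up much of a table row.

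**Working it through.** Section 11.5 gives no figure, so there is none to reproduce. The check has two parts.

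**1. Can an eligible man start inside a toxicity row?**

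- Hemoglobin: entry is allowed from 10 g/dL; the anemia row applies below 110, taken as g/L, which is 11.0 g/dL. Values from 10.0 to below 11.0 g/dL meet both. Yes.
- AST/ALT: entry is allowed to 1.5 times the upper limit; the hepatic row of Section 5.5.1 starts at 1.8 times. Values above normal are eligible but do not reach that row. Whether they receive a CTCAE grade cannot be read from the documents, which do not print the cut-points.
- Bilirubin: normal at entry. No overlap.

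**2. What does this do to an any-grade row?**

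Inputs: 22 and 44 men at full accrual (Section 11.1, nominal 2:1 split of 66). The share b already abnormal at entry is not in the documents; the assumed range is 5-30%. The on-study risks pA = 5% and pB = 20% are illustrative assumptions. (Section 11.2 uses the same two percentages for arm B DLT rates, a different quantity.)

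Raw any-grade rate = b + (1-b)p. Arm difference = (1-b)(pB - pA). Chance imbalance in baseline prevalence has SD = sqrt[b(1-b)(1/22 + 1/44)].

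For b = 15%: arm A is 0.15 + 0.85 x 0.05 = 19.3%; arm B is 0.15 + 0.85 x 0.20 = 32.0%. The difference is 0.85 x 15 = 12.8 points and the ratio 32.0/19.3 = 1.7. The SD is sqrt(0.1275 x 0.0682) = 9.3 points.

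| b (assumed) | Raw A | Raw B | Difference | Ratio | Pre-existing share of raw A | SD of imbalance |
|---|---|---|---|---|---|---|
| 0 | 5.0% | 20.0% | 15.0 | 4.0 | 0% | 0 |
| 5% | 9.8% | 24.0% | 14.2 | 2.5 | 51% | 5.7 |
| 15% | 19.3% | 32.0% | 12.8 | 1.7 | 78% | 9.3 |
| 30% | 33.5% | 44.0% | 10.5 | 1.3 | 90% | 12.0 |

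The b = 0 row is also what a baseline-referenced table would show if p applies to every man, as new onset in those normal at entry and as worsening in those already abnormal. The raw any-grade row cannot show that worsening, because those men are already counted. If men abnormal at entry never worsened, the referenced rates over all men would be (1-b)p. The difference would then be the same in both tables, and the gain would lie in the ratio (back to 4.0) and in less noise.

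On noise, the arm difference has an ordinary sampling SD even with perfect baseline reference: sqrt(0.05 x 0.95/22 + 0.20 x 0.80/44) = 7.6 points. For the raw table at b = 15% it is sqrt(0.1925 x 0.8075/22 + 0.32 x 0.68/44) = 11.0 points. The addition is therefore from 7.6 to 11.0.

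**The case against.** The best defence is that Section 11.5 is silent on baseline rather than opposed to it. A competent analyst might add a shift table anyway, and the laboratory measurements to be tabulated are only described as selected. That is fair. But the stated rule, followed as written, takes no account of the starting value, and leaving the choice open until the data are seen is the weaker position.

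The second defence also stands: no between-arm safety comparison is planned. The safety objective in Section 2.2 is not worded as a comparison with bicalutamide alone, unlike several of its neighbours, and Section 11.5 plans no test or risk ratio. The ratios above describe what a reader would see in the table, not a planned analysis. The model is also a simplification, since it collapses grades to abnormal or not and lets mild values count in full. Summarizing adverse events by causal relationship helps for events but not for the laboratory table.

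Three stronger readings are tempting, and the documents do not support them:

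- *That liver values are the main problem, because Section 9.2.10 links bicalutamide to liver injury.* No eligible man starts inside a hepatic row of Section 5.5.1.
- *That chance imbalance at baseline rivals a true effect.* Its SD of 5.7 to 12.0 points is below the assumed 15-point effect throughout the range.
- *That symptoms could be handled in the same way at no cost.* Table 1 has a review of systems at screening but no adverse event recording there, so graded baseline symptoms are not shown to exist.

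**Conclusion.** The point holds as a minor one about descriptive laboratory tables. Section 11.5 as written would count unchanged mild abnormalities present at entry as toxicity in both arms. That inflates the rates and reduces the visible any-grade arm difference by the factor (1-b), a loss of 5-30% if b is 5-30%. It rests on a literal reading of Section 11.5, on reading 110 as g/L, on an assumed b, and on men already abnormal being as likely to worsen as others are to become abnormal.

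A reader might infer that the arm comparison is biased. It is not: randomization gives both arms the same b in expectation, so the effect is dilution and noise. Entry limits keep most pre-existing abnormalities mild, so severe-grade tables should change little. The primary endpoint and sample size are unaffected, and the rule in Section 11.2 counts DLTs in arm B rather than entries in this table.

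**What to change.** Add to Section 11.5:

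> Baseline is the last laboratory value before the start of cycle 1 in both arms. The worst post-baseline grade will be tabulated against the baseline grade by arm, and only grades above the subject's own baseline grade will be counted as on-study laboratory toxicity.

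On-study is the safer term than treatment-emergent, because arm A is observed without treatment in cycles 1 and 2 while arm B takes metformin; a common starting point keeps the windows equal. Limit the rule to laboratory measurements already taken at screening (CBC, chemistry, vitamin B12 and the others in Table 1). State the hemoglobin unit used for grading.

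The cost is one sentence and one table layout. No new data or visits are needed, and no treatment rule changes. It carries into the analysis the principle that Sections 5.5 and 5.9 already apply.

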12.0 DATA SAFETY MONITORING PLAN

12.1 Monitoring Plan

FCCC ISRU will monitor the medical and study records of each participant accrued throughout the course of the study. In addition, the ISRU will collect and report data to the study Sponsor-Investigator who will review these data on a regular basis at a rate dependent on subject accrual. All serious adverse events (SAEs) will be reviewed on a real time basis first by the study site PI and subsequently by the ISRU and Sponsor-Investigator as applicable.

12.2 Data Safety Monitoring Board

Interim analysis of toxicity, outcome and ongoing scientific investigations will be performed at least every 6 months by the Fox Chase Cancer Center Data Safety Monitoring Board (FCCC DSMB). In this capacity the FCCC DSMB will serve as an advisory committee to the Sponsor-Investigator. The FCCC DSMB will review those aspects of this trial that are outlined in the responsibilities section of the Data and Safety Monitoring Plan (DSMP). If the committee decides that changes should be made to this trial, it will make recommendations in writing to the Sponsor-Investigator, the Associate Director of Clinical Research, and the Protocol Management Executive Committee, which, in turn, have the authority to approve or disapprove these recommendations. These changes will be discussed with the Sponsor-Investigator before they are implemented. These changes may include early termination of accrual. Other changes might include altering the accrual goals or changing the eligibility criteria for the trial.

13.0 Administrative

This study will be conducted in accordance will local, state and Federal regulations and according to accepted good clinical practice guidelines.

13.1 Data Reporting

The FCCC Study Monitor will request case report forms to be completed within 2 weeks of the protocol visit. Participating sites are responsible to respond to queries prior to the next scheduled monitoring visit.

The ISRU is responsible for compiling and submitting data to the Sponsor-Investigator and statistician on an ongoing basis for monitoring as described in the data safety monitoring plan and reporting to the Data and Safety Monitoring Board.

All patient information will be stored in an EDC system accessible only to the study team members for the purpose of entering, reviewing and analyzing data. Any paper records, such as case report files, produced will be stored in a secure location.

The ISRU is responsible for distributing and tracking review of all IND Action Letters, Safety Reports, study specific Serious Adverse Events.

13.2 Retention of Records

Time points for the retention of records are described in detail in the contract between the grantor and the OCR and passed on to the participating site. Please refer to the study specific terms for specific time points. In all cases the Study Monitor must be notified of any plans to move records to an offsite location prior to doing so.

13.3 Study Agents

Any study agent supplied through the OCR from the manufacturer or a third party distributor may not be used for any purpose outside the scope of this protocol. The agent may not be transferred to any party not participating in the clinical trial.

13.4 Informed Consent

The IRB approved informed consent documents must be signed by the patient, or the patient's legally authorized representative, before his or her participation in the study. The case history for each patient shall document that informed consent was obtained prior to participation in the study. A copy of the informed consent documents must be provided to the patient or the patient's legally authorized representative. If applicable, they will be provided in a certified translation of the local language.

Original signed consent forms must be filed in each patient's study file or medical record with a copy in the study file.

APPENDIX I

Diary for _____ dosing.

(Name of Study Drug)

Study Participant's Initials _____ Sequence # _____ Cycle # _____

Instructions

Please complete this diary when taking your _____. Your prescribed dose is _____.

_____ should be taken orally _____ day for _____ days. You should take your dose at approximately the same time every day.

_____ should be taken with / without (choose one or edit) food.

If you miss a dose, record this in your diary. Doses should not be doubled to make up for missed doses. If you vomit after taking a dose, record this in your diary. Do not take an additional dose to make up for this dose.

Bring your empty container or unused pills back to the hospital at the end of each cycle of treatment. There are certain medications that are prohibited while you are on this study. Please let your physician or protocol nurse know about all medications you are taking, and check with them before beginning any new medications.

If you have any questions, please contact your protocol coordinator _____ at _____.

Study Participant's Initials _____ Sequence # _____ Cycle # _____

Study Drug Name _____

Day	Date	Time	Dose	Reason, if dose not taken
1				
2				
3				
4				
5				
6				
7				
8				
9				
10				
11				
12				
13				
14				
15				
16				
17				
18				
19				

20				
----	--	--	--	--

21				
22				
23				
24				
25				
26				
27				
28				

Date _____ Study Participant Signature _____

Study Participant's Initials _____ Sequence # _____ Cycle # _____

SECTION TO BE COMPLETED BY CLINICAL RESEARCH COORDINATOR	
Total # of pills dispensed _____	Date _____
Total # of pills returned _____	Date _____
CRC Signature _____	Date _____

APPENDIX II

Below is a list of statements that other people with your illness have said are important. **Please circle or mark one number per line to indicate your response as it applies to the past 7 days**

PHYSICAL WELL-BEING		Not at all	A little bit	Some- what	Quite a bit	Very much
GP1	I have a lack of energy	0	1	2	3	4
GP2	I have nausea	0	1	2	3	4
GP3	Because of my physical condition, I have trouble meeting the needs of my family	0	1	2	3	4
GP4	I have pain.....	0	1	2	3	4
GP5	I am bothered by side effects of treatment	0	1	2	3	4
GP6	I feel ill.....	0	1	2	3	4
GP7	I am forced to spend time in bed.....	0	1	2	3	4

SOCIAL/FAMILY WELL-BEING		Not at all	A little bit	Some- what	Quite a bit	Very much
GS1	I feel close to my friends.....	0	1	2	3	4
GS2	I get emotional support from my family	0	1	2	3	4
GS3	I get support from my friends	0	1	2	3	4
GS4	My family has accepted my illness	0	1	2	3	4
GS5	I am satisfied with family communication about my illness	0	1	2	3	4
GS6	I feel close to my partner (or the person who is my main support)	0	1	2	3	4
Q1	Regardless of your current level of sexual activity, please answer the following question. If you prefer not to answer it, please mark this box and go to the next section.					

GS7	I am satisfied with my sex life	0	1	2	3	4
-----	---------------------------------------	---	---	---	---	---

Please circle or mark one number per line to indicate your response as it applies to the past 7 days.

EMOTIONAL WELL-BEING

		Not at all	A little bit	Some-what	Quite a bit	Very much
GE1	I feel sad.....	0	1	2	3	4
GE2	I am satisfied with how I am coping with my illness.....	0	1	2	3	4
GE3	I am losing hope in the fight against my illness.....	0	1	2	3	4
GE4	I feel nervous.....	0	1	2	3	4
GE5	I worry about dying.....	0	1	2	3	4
GE6	I worry that my condition will get worse	0	1	2	3	4

FUNCTIONAL WELL-BEING

		Not at all	A little bit	Some-what	Quite a bit	Very much
GF1	I am able to work (include work at home)	0	1	2	3	4
GF2	My work (include work at home) is fulfilling.....	0	1	2	3	4
GF3	I am able to enjoy life	0	1	2	3	4
GF4	I have accepted my illness	0	1	2	3	4
GF5	I am sleeping well	0	1	2	3	4
GF6	I am enjoying the things I usually do for fun.....	0	1	2	3	4
GF7	I am content with the quality of my life right now	0	1	2	3	4

Please circle or mark one number per line to indicate your response as it applies to the past 7 days.

ADDITIONAL CONCERNS		Not at all	A little bit	Some-what	Quite a bit	Very much
C2	I am losing weight	0	1	2	3	4
C6	I have a good appetite.....	0	1	2	3	4
P1	I have aches and pains that bother me.....	0	1	2	3	4
P2	I have certain parts of my body where I experience pain....	0	1	2	3	4
P3	My pain keeps me from doing things I want to do.....	0	1	2	3	4
P4	I am satisfied with my present comfort level	0	1	2	3	4
P5	I am able to feel like a man	0	1	2	3	4
P6	I have trouble moving my bowels	0	1	2	3	4
P7	I have difficulty urinating.....	0	1	2	3	4
BL2	I urinate more frequently than usual.....	0	1	2	3	4
P8	My problems with urinating limit my activities.....	0	1	2	3	4
BL5	I am able to have and maintain an erection	0	1	2	3	4

Patient Name _____

Signature _____

Date _____
